### 6.6.3 Hematologic and Infectious Toxicities

Optimal supportive care should be offered to the patient in order to mitigate toxicities. Where appropriate, this includes administration of G-CSF, GM-CSF and blood/platelet transfusions as per institutional guidelines. At the start of each cycle, hold therapy until ANC  $\geq$ 500/mm^3 and platelet count is  $\geq$ 25,000/mm^3. Lymphopenia is an expected toxicity of CLL treatments and therefore should be graded and recorded as per CTCAE v5.0, but treatment holds and dose changes are not needed.

This study will utilize the 2018 IWCLL grading scale for hematologic adverse events in patients with baseline platelet count <100,000/mm^3 and/or baseline hemoglobin less than the lower limit of normal. Grading of ANC is at the nadir within the cycle, and patients who have an ANC <1 x  $10^{9}$ /L before therapy will not be evaluable for toxicity. These criteria account for baseline cytopenias secondary to CLL and are detailed in Table 12 below.

Grade	Decrease in platelets or hemoglobin from baseline value, %	Absolute neutrophil count* (nadir) x 10  /L
0	No change to 10	≥2
1	11-24	≥1 and <2
2	25-49	≥1 and <1
3	50-74	≥0.5 and <1
4	≥75	<0.5

Table 12. iwCLL Hematologic Grading

\*If the absolute neutrophil count (ANC) reaches  $<1 \times 10^{9}$ /L, it should be judged to be grade 3 toxicity. Other decreases in the white blood cell count or in circulating granulocytes are not to be considered because a decrease in the white blood cell count is a desired therapeutic end point. A gradual decrease in granulocytes is not a reliable index in CLL for stepwise grading of toxicity. If the ANC was  $<1 \times 10^{9}$ /L before therapy, the patient is not evaluable for toxicity referable to the ANC. The use of G-CSF is irrelevant for the grading of toxicity, but should be documented.

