Grade 3	Hold until platelets ∫ ≥50,000/mm  . At first occurrence, no change in dose or dosing schedule. If toxicity recurs, follow reductions in dosing schedule and drug dosages as per sections 6.6.1 and 6.6.2.	Hold until platelets J ≥50,000/mm  . At first occurrence, no change in dose or dosing schedule. If toxicity recurs, follow reductions in dosing schedule and olaparib dosages as per sections 6.6.1 and	

		decreased for the same toxicity.
Grade 4	Same management as grade 3	Same management as grade 3
	0 -	

∫Only for patients with baseline platelets ≥100,000/mm^3. For patients with baseline platelets <100,000/mm^3, hold until platelets have recovered to at least 50% of baseline value.

Event Name	Neutropenic Fever	
Grade of Event	Management/Next Dose for RP - 3500	Management/Next Dose for Olaparib
Grade 3	Hold until resolution of toxicity. G- CSF administration required. At first occurrence, no change in dose or dosing schedule. If toxicity recurs, follow reductions in dosing schedule and drug dosages as per sections 6.6.1 and 6.6.2.	Hold until resolution of toxicity. G- CSF administration required. At first occurrence, no change in dose or dosing schedule. If toxicity recurs, follow reductions in dosing schedule and olaparib dosages as per sections 6.6.1 and 6.6.2 if RP-3500 dosage already decreased for the same toxicity.

Grade 4	Hold until resolution of toxicity. G- CSF administration required. Follow reductions in dosing schedule and olaparib dosages as per sections 6.6.1 and 6.6.2.	Hold until resolution of toxicity . G- CSF administration required. Follow reductions in dosing schedule and olaparib dosages as per sections 6.6.1 and 6.6.2.if RP- 3500 dosage already decreased for the same toxicity.
Event Name	Ane	mia
Treat per institutional guidelines including blood transfusions and/or erythropoietins. Consider transfusing for symptoms with hemoglobin >8 g/dL (Grade <3) or for any Grade 3 (hemoglobin		

transfusing for symptoms with hemoglobin >8 g/dL (Grade <3) or for any Grade 3 (hemoglobin <8 g/dL). If possible, maintain RP-3500 and olaparib doses as long as patient is clinically stable, but if a dose reduction or interruption is desired, consult with the Medical Monitor.

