#### 8.2 Adverse Event Reporting

The investigator and qualified designees are responsible for the detection, documentation, reporting, and follow-up of all adverse events experienced by subjects during trial participation. AEs and SAEs will be recorded from the initiation of study therapy until 28 days after the last dose of study medication or until new cancer therapy is started. The following information will be required for each adverse event:

- Event term;
- For non-hematologic toxicities and patients with normal baseline platelet, hemoglobin and ANC, event severity as graded by the CTCAE v.5;
- For patients with baseline cytopenias (i.e. platelet count <100,000/mm^3 and/or hemoglobin less than the lower limit of normal), hematologic toxicity event severity as graded by 2018 iwCLL criteria (Refer to section 6.6.3)
- The causality assessment to study medication per the below definitions;
- Expectedness;
- Event duration;
- Any action taken to treat or manage the event;
- Event outcome.

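### Low hemoglobin alone puts platelets with a baseline above 100,000 on the percent-fall scale, so grade 3 begins above Table 13's own 50,000 release level and conflicts with the CTCAE rule stated elsewhere

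*Combined protocol and SAP*

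**What the plan says.** **Which scale applies.** Section 6.6.3: "This study will utilize the 2018 IWCLL grading scale for hematologic adverse events in patients with baseline platelet count" under 100,000/mm³ "and/or baseline hemoglobin less than the lower limit of normal". Section 8.2 restates it: "For patients with baseline cytopenias (i.e. platelet count" under 100,000/mm³ and/or low hemoglobin), with "hematologic toxicity event severity as graded by 2018 iwCLL criteria". The companion bullet in 8.2 reads: "For non-hematologic toxicities and patients with normal baseline platelet, hemoglobin and ANC, event severity as graded by the CTCAE v.5".

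**What the scale does.** Table 12 grades by "Decrease in platelets or hemoglobin from baseline value": a 50–74% fall is grade 3 and a fall of 75% or more is grade 4. Neutrophils are treated differently ("Grading of ANC is at the nadir within the cycle", against absolute cuts), and 6.6.3 leaves lymphopenia on CTCAE.

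**What the grade triggers.** Table 13 holds both drugs at grade 3 thrombocytopenia until platelets reach 50,000/mm³. A first event brings no change and a recurrence brings reductions. Grade 4 is managed the same way. The footnote assigns the 50,000 level by platelet baseline alone ("Only for patients with baseline platelets ≥100,000/mm", the unit being per mm³). Patients with lower baselines are held until platelets recover to half of baseline.

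**Other grading rules.** The platelet DLT criterion in 4.2.4 also splits by platelet baseline alone: below 25,000 for at least 7 days if baseline is 100,000 or more, otherwise a fall of at least 75% for that time. The safety endpoint (2.2.1), the general grading sentence of 4.2.4, the severity section (8.2.1) and the safety analysis (9.5.1) all name CTCAE version 5 and mention no iwCLL exception.

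**The concern.** Section 6.6.3 says the percent-fall scale is there to allow for cytopenias that CLL has already caused. Because the trigger is per patient and joined by and/or, it also reaches a lineage that is not low at baseline. An anemic patient with platelets of 200,000 has them graded by percent fall.

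Two things are at stake. First, Table 13 can call for a hold when the condition for lifting it is already satisfied, and a second such event sends the patient down the reduction path. Second, the scale used for AE reporting (8.2) is not the one named for the safety endpoint and its analysis (2.2.1, 9.5.1), so reported severity depends on which section the analyst follows.

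Grades on the iwCLL scale already inform decisions here. Section 4.1 cites grade 4 thrombocytopenia by iwCLL criteria in 2 of 5 patients among the reasons for changing the schedule, while one patient met the DLT definition. The baselines of those patients are not given, so nothing can be said about whether they were misgraded.

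**Working it through.** **Inputs.** Table 12: grade 3 is a 50–74% fall and grade 4 a fall of 75% or more. Table 13: release at 50,000 for platelet baseline ≥100,000. Section 4.2.4: absolute grade 4 cut of 25,000 for the same group. The baselines B below are illustrative, because the documents give no platelet distribution.

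**Formulas.** Grade 3 begins at 0.50 × B. Its lower end is 0.26 × B (a 74% fall). Grade 4 begins at 0.25 × B.

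**Where the rules agree.** The 50,000 level is a set threshold, so there is no figure to reproduce, but it can be checked for consistency. At B = 100,000:

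- 0.50 × 100,000 = 50,000, the Table 13 release level.
- 0.25 × 100,000 = 25,000, the grade 4 cut in 4.2.4.

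Below 100,000, Table 13 releases at half of baseline, exactly where Table 12 starts grade 3. Trigger and release therefore match for patients with low platelets, and the percent and absolute rules meet at 100,000. They separate only above it.

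**Above 100,000, with low hemoglobin.**

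| Baseline B | Grade 3 begins (0.50 × B) | Grade 4 begins (0.25 × B) |
|---|---|---|
| 120,000 | 60,000 | 30,000 |
| 150,000 | 75,000 | 37,500 |
| 200,000 | 100,000 | 50,000 |
| 250,000 | 125,000 | 62,500 |
| 300,000 | 150,000 | 75,000 |

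**Thresholds.**

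- Some of grade 3 lies above 50,000 when 0.50 × B > 50,000, so B > 100,000.
- All of grade 3 does when 0.26 × B > 50,000, so B > 50,000 / 0.26 ≈ 192,300. If the band is read as running up to just under 75%, this becomes 200,000.
- Part of grade 4 does when 0.25 × B > 50,000, so B > 200,000.

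**Examples.**

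- 150,000 to 70,000: fall 80/150 = 53%, grade 3.
- 200,000 to 90,000: fall 110/200 = 55%, grade 3.
- 250,000 to 60,000: fall 190/250 = 76%, grade 4.

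In each case the count already exceeds the release level when the hold is triggered. The last count is grade 4 on Table 12 but not on the 25,000 cut in 4.2.4. The documents do not reproduce the CTCAE bounds for grade 3 platelets, so the corresponding grade 3 comparison is not made.

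**The case against.** The strongest reply is that CTCAE is the stated default in 2.2.1, 4.2.4, 8.2.1 and 9.5.1, so the safety endpoint is not distorted at all. If the analyst follows 9.5.1, that is right, and a reader who infers an inflated grade 3–4 thrombocytopenia endpoint goes too far. No such rate is a named endpoint. What stands is that 8.2 instructs sites to record a different grade from the one 9.5.1 says will be analysed.

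Other inferences the documents do not support:

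- **That every blood count switches.** Only platelets and hemoglobin move to percent fall. Neutrophils stay on absolute nadirs and lymphocytes on CTCAE.
- **That the MTD or trial stopping is affected.** The platelet DLT rule carries its own absolute cut, the MTD rests on DLT rates (4.2.3), and section 9.3 counts only non-hematologic events. The only route to the RP2D is the review of cumulative safety in 4.2.3.
- **That a patient with platelets between 100,000 and the lower limit of normal, and normal hemoglobin, has no scale.** The two bullets in 8.2 do omit this patient, but the general CTCAE rule in 8.2.1 applies.
- **That dose intensity falls.** A first event changes nothing and the hold can lift at once. Modifications are described as suggestions to be individualized (6.5), and re-escalation is allowed (6.6.3).

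Section 8.1.1 also keeps laboratory findings out of AE reporting unless they cause symptoms, need intervention, change dosing or are judged to be an AE. That narrows the effect but does not remove it, because a reduction under Table 13 would itself meet the dosing condition.

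**Conclusion.** The inconsistency is real and follows from the text. For a patient with low hemoglobin and a platelet baseline above 100,000, sections 6.6.3 and 8.2 place the start of grade 3 at half of baseline, always above the 50,000 at which Table 13 lifts the hold. All of grade 3 lies above that level from a baseline of about 192,000, and part of grade 4 from 200,000. Separately, the same count can carry one grade in AE reporting and another in the safety analysis.

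This assumes that the patient-level trigger is read literally and that the grades in Table 13 are those of Table 12, which stands in the same section. The arithmetic needs no distributional assumption. A trial-level size cannot be given: the documents report neither platelet baselines and nadirs nor the share of patients with low hemoglobin and platelets of 100,000 or more. The point concerns the clarity of safety grading and of one management table. It does not threaten either primary endpoint analysis, but it should be corrected before safety data are tabulated.

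**What to change.** State one grading rule for AE reporting and safety tables, in the same terms in 6.6.3, 8.2, 8.2.1, 9.5.1 and the safety endpoint (2.2.1 and the synopsis), and align the general CTCAE sentence in 4.2.4. Grading each lineage by its own baseline would be consistent with the platelet DLT rule and the Table 13 footnote: percent fall for platelets only when baseline platelets are below 100,000, percent fall for hemoglobin only when baseline hemoglobin is below the lower limit of normal, and CTCAE version 5 otherwise.

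Separately, ask the sponsor to reconcile the grade that triggers the Table 13 platelet hold with the level that releases it, for patients with low hemoglobin and platelet baseline of 100,000 or more. Which clinical rule should govern is for the sponsor to decide.

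The cost is rewording a few sentences in an amendment. Grades already assigned can be rederived from the blood counts collected under the Schedule of Events, with no new data.

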## 4.2.2 Dose Escalation

During dose escalation, four DLs of combination therapy of RP-3500 and olaparib may be explored (Table 7. Dose levels of RP-3500 and olaparib in phase Ib portion of the trial.). Subjects will be enrolled in cohorts of three starting with DL 1. Enrollment will be placed on hold to allow for all members of a cohort to complete the Dose Limiting Toxicity (DLT) period. Once all subjects in a cohort have completed the defined DLT evaluation period, the assignment of the dose level for the following cohort will follow the decision algorithm in Table 8. Dose escalation rules according to the keyboard phase I design. Doses may be escalated (E) to the next highest dose level, de-escalated (D) to a lower dose level, or stay (S) at the same dose level (Table 8. Dose escalation rules according to the keyboard phase I design.).

Table 7. Dose levels of RP-3500 and olaparib in phase Ib portion of the trial.

Dose Level	RP-3500	Olaparib
-1#	40mg daily	100mg BID
1*	50mg daily	100mg BID
2*	80mg daily	100mg BID
3*	80mg daily	150mg BID

As long as there are not any unacceptably (U) high toxicities encountered with the enrolled patients as according to the keyboard algorithm, then the trial can continue enrollment in cohorts of 3 patients. Each cohort will complete the DLT window at which point it will trigger the Data Safety Monitoring Committee (DSMC) and the Principal Investigator of the trial to convene and determine the appropriate DL for the following cohort(s). The DSMC and Principal Investigator can also make the recommendation to enroll in cohorts of 1-2 patients if a slower enrollment is required to ensure the safety of the drug combination. All patients enrolled in these smaller cohorts must complete the DLT window prior to the determination of the number of patients to enroll in the next cohort and at which DL. Should a DL accumulate enough DLTs so that the keyboard algorithm dictates a U, the remaining cohorts will be de-escalated to the next lowest DL and no more patients will be treated at the DL with U toxicities.

Table 8. Dose escalation rules according to the keyboard phase I design.

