### 6.5 Dose Reductions

In dose-escalation, toxicities that occur within the DLT window that are deemed DLTs (Section 4.1.3 Definition of Dose Limiting Toxicities) will result in protocol removal. Adverse events that are not defined as DLTs, or occur after the DLT window, or occur in patients enrolled in the dose-expansion cohort may lead to dose delays and modifications as detailed in section 6.6. No dose reduction below RP-3500 20mg daily and olaparib 100mg BID will be allowed. Should the protocol dictate a dose reduction of olaparib below 100mg BID and/or RP-3500 below 20mg daily, the patient will be taken off of the protocol therapy. While these are suggested dosing schedule modifications and dosage reductions, the optimal dosing and dosing schedule for each patient should be individualized, and may not always fall into a step-wise fashion. Consultation with the study PI and medical monitor is recommended to determine the optimal dosing for each patient after significant AEs.

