## Table 10.: Dosing Schedule Modifications

Dose Level	Schedule (21 -Day Cycles)	Camonsertib (RP -3500) and Olaparib dosing
Starting	3 weeks on	2 days on/5 days off
-1	2 weeks on/1 week off	2 days on/5 days off during dosing weeks
-2	1 week on/2 weeks off	3 days on/4 days off during dosing weeks

Should the patient require further dose reductions for toxicities, decreases in either camonsertib and/or olaparib dosages can be considered while maintaining the current dosing schedule or concurrently with a dosage decrease and a change in the dosing schedule. The study PI and medical monitor should be contacted for help in determining optimal dosing and dosing schedule for the patient. Some example patient scenarios are presented below:

- Patient experiences grade 3 neutropenic fever for a second time while receiving camonsertib (RP-3500) 50mg daily and olaparib 150mg BID on a dosing schedule of 2 days per week every week (i.e. no off weeks). Dose reduction of camonsertib to 40mg daily and olaparib to 100mg BID can be considered while maintaining the 2 days per week every week (i.e. no off weeks) dosing schedule.
- Patient experiences grade 4 neutropenic fever while receiving camonsertib (RP-3500) 50mg daily and olaparib 150mg BID on a dosing schedule of 2 days per week every week (i.e. no off weeks). Dose reduction of camonsertib to 40mg daily and olaparib to 100mg BID along with reduction of the dosing schedule to 2 weeks on/1 week off may be considered while maintaining the 2 days per week treatment during the dosing/on weeks.

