## 6.6.2 Drug Dosage Modifications

After dosing schedule modifications, dosage reductions of either camonsertib and/or olaparib can considered independently or concurrently with dosing schedule modifications. If either camonsertib (RP-3500) or olaparib requires reductions to below DL 1 for toxicity management, study therapy will be discontinued:

Table 11. Dose Reduction Levels

Dose Level	Camonsertib(RP-3500)
1	20mg daily
2	30mg daily

3	40mg daily
4	50mg daily
5	80mg daily

Dose Level	Olaparib
1	100mg BID
2	150mg BID

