The order in which dose reductions will occur will be change in dosing schedule (Table 10.: Dosing Schedule Modifications) with either sequential (preferred) or concurrent changes in drug dosages (Table 11). If drug dosage changes are required, the order in which dose reductions will occur will be camonsertib (RP-3500) first followed by olaparib if the AE continues to occur. If at any time a dose reduction would leave camonsertib (RP-3500) or olaparib doses less than DL 1 (Table 11. Dose Reduction Levels), the patient will be taken off protocol. Treatment delays for adverse events exceeding 21 days will lead to protocol removal. If reduction of the dosing schedule and/or drug doses resolves the patient's toxicity to grade  $\leq 1$  for at least 3-6 weeks, increasing camonsertib (RP-3500) and/or olaparib back to the prior dose or dosing schedule is permitted after discussion with the study PI.

Event Name	Neutropenia	
Grade of Event	Management/Next Dose for RP - 3500	Management/Next Dose for Olaparib
≤ Grade 1	No change in dose	No change in dose
Grade 2	No change in dose	No change in dose
Grade 3	No change in dose	No change in dose
Grade 4	Hold until ANC ∫ is ≥1000/mm  . G- CSF administration is recommended. At first occurrence, no change in dose or dosing schedule. If toxicity recurs, follow reductions in dosing schedule and drug dosages as per sections 6.6.1 and 6.6.2 only if grade 4 neutropenia lasts ≥7 days with optimal supportive care.	Hold until ANC ∫ is ≥1000/mm  . G- CSF administration is recommended. At first occurrence, no change in dose or dosing schedule. If toxicity recurs, follow reductions in dosing schedule and drug dosages as per sections 6.6.1 and 6.6.2 only if grade 4 neutropenia lasts ≥7 days with optimal supportive care and

Table 13. Management and dose modification guidelines for hematologic toxicities encountered with combination camonsertib (RP-3500) and olaparib.

6.6.2 if RP-3500 dosage already

		RP-3500 dosage already decreased for the same toxicity.	
j Only for patients with ANC $\geq$ 500/mm 	 Only for patients with baseline ANC $\geq$ 1000. For patients with baseline ANC <1000, hold until ANC $\geq$ 500/mm 		
Event Name	Thromboc	ytopenia	
Grade of Event	Management/Next Dose for RP - 3500	Management/Next Dose for Olaparib	
≤ Grade 1	No change in dose	No change in dose	
Grade 2	No change in dose	No change in dose	

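### Table 13, grade 4 neutropenic fever: the RP-3500 cell calls for an olaparib dosage cut, against the olaparib cell beside it and the RP-3500-first order in section 6.6.3

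*Combined protocol and SAP*

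**What the plan says.** Table 13 in section 6.6.3 has one column for the next RP-3500 dose and one for the next olaparib dose. For grade 4 neutropenic fever, both columns hold drug until resolution and require G-CSF.

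- **RP-3500 column:** the site is then to "follow reductions in dosing schedule and olaparib dosages as per sections 6.6.1 and 6.6.2". No condition is attached.
- **Olaparib column:** the same instruction appears, but it applies only if the RP-"3500 dosage already decreased for the same toxicity".

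The text above the table fixes the sequence once a dosage change is needed: "the order in which dose reductions will occur will be camonsertib (RP-3500) first followed by olaparib if the AE continues to occur".

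Two provisions set the floor. Section 6.5: "Should the protocol dictate a dose reduction of olaparib below 100mg BID and/or RP-3500 below 20mg daily, the patient will be taken off" protocol therapy. Section 6.6.2: "If either camonsertib (RP-3500) or olaparib requires reductions to below DL 1 for toxicity management, study therapy will be discontinued". In that sentence DL 1 is the bottom row of Table 11 (RP-3500 20 mg daily, olaparib 100 mg BID), not dose level 1 of the escalation in Table 7.

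Section 6.6.1 gives a worked example for this same event: "Patient experiences grade 4 neutropenic fever while receiving camonsertib (RP-3500) 50mg daily and olaparib 150mg BID". There RP-3500 goes to 40 mg daily and olaparib to 100 mg BID, together with a schedule change to 2 weeks on and 1 week off.

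**The concern.** An RP-3500 cell that names olaparib dosages gives RP-3500 no mg step of its own. The two cells of the row then disagree for any patient whose RP-3500 has not yet been lowered: one calls for an olaparib cut and the other withholds it. The olaparib cell's condition also presupposes an RP-3500 reduction that its neighbour never orders.

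This is an operative rule after a life-threatening event. Unlike the grade 3 row, it has no step that leaves dose and schedule unchanged at first occurrence, so it applies from the first episode. Once the dosage step is reached, a site that follows the cell lowers olaparib and keeps RP-3500 at full mg dose. Where olaparib is already at its floor, the same instruction takes the patient off study therapy while RP-3500 could still be lowered.

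The row governs phase II, and phase Ib after the DLT window. Inside the window, febrile neutropenia of any grade is a DLT (section 4.2.4) and leads to protocol removal (section 6.5).

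**Working it through.** **1. The cell against the rest of the protocol**

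| Place | What is reduced in mg, and when |
|---|---|
| Table 13, grade 4 neutropenic fever, RP-3500 cell | Olaparib, no condition |
| Same row, olaparib cell | Olaparib, only if RP-3500 already reduced for this toxicity |
| Section 6.6.3 text | RP-3500 first, then olaparib if the event continues |
| Table 13, RP-3500 cells for grade 4 neutropenia, grade 3 thrombocytopenia and grade 3 neutropenic fever | Drug dosages, not olaparib dosages |
| Section 6.6.1, grade 4 neutropenic fever example | Both drugs together |

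None of the other entries supports an unconditional cut to olaparib alone. The three comparator cells suggest that the wording was copied across from the olaparib column. That is an inference; the contradiction itself is on the page.

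**2. Inputs for the size**

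- Assigned doses: Table 7 ("Dose levels of RP-3500 and olaparib in phase Ib portion of the trial"). RP-3500 is 40, 50, 80 and 80 mg daily at dose levels -1, 1, 2 and 3. Olaparib is 100, 100, 100 and 150 mg BID.
- Schedule: Table 10. The start is 2 days per week for 3 weeks. Level -1 is 2 days per week for 2 of 3 weeks.
- Dosage ladders: Table 11. RP-3500 is 20, 30, 40, 50, 80 mg daily; olaparib is 100, 150 mg BID.

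**3. Dose level 3, schedule level -1 plus one dosage step**

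Dosing days per 21-day cycle: start 2 × 3 = 6; schedule level -1, 2 × 2 = 4. Cycle dose = daily dose × dosing days, with olaparib 150 mg BID = 300 mg per day and 100 mg BID = 200 mg per day.

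| | RP-3500 per cycle | Olaparib per cycle |
|---|---|---|
| Starting dose and schedule | 80 × 6 = 480 mg | 300 × 6 = 1800 mg |
| Cell as written (olaparib 150 to 100 mg BID) | 80 × 4 = 320 mg | 200 × 4 = 800 mg |
| Section 6.6.3 order (RP-3500 80 to 50 mg) | 50 × 4 = 200 mg | 300 × 4 = 1200 mg |

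Ratios, cell to section 6.6.3 order: RP-3500 320/200 = 1.6; olaparib 800/1200 = 0.67. The dosing days cancel, so the ratios do not depend on the schedule level. The mg totals are the same whether the schedule and dosage steps are taken together or one after the other.

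**4. Levels left below the assigned dose (Table 11)**

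| Dose level | Olaparib levels left | RP-3500 levels left |
|---|---|---|
| -1 | 0 | 2 (30, 20 mg) |
| 1 | 0 | 3 (40, 30, 20 mg) |
| 2 | 0 | 4 (50, 40, 30, 20 mg) |
| 3 | 1 (100 mg BID) | 4 (50, 40, 30, 20 mg) |

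At 3 of the 4 planned levels an olaparib step is a step below the floor, which sections 6.5 and 6.6.2 treat as the end of study therapy.

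**The case against.** The best answer is that the cell rarely acts alone. It points to sections 6.6.1 and 6.6.2, and 6.6.1 changes the schedule before any dosage. Section 6.6.3 prefers sequential to concurrent changes. So on the preferred route a first grade 4 event produces a schedule step, with no olaparib mg cut and no discontinuation, and that step does reduce RP-3500 dosing days. Section 6.6.2 lets either drug be lowered. Section 6.5 calls the reductions suggestions to be individualized and recommends consulting the study PI and medical monitor. A careful site also has the section 6.6.3 text, the neighbouring cell's condition and the section 6.6.1 example all pointing toward lowering RP-3500.

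The size also depends on the comparator. If both drugs are cut one step at dose level 3, as in the section 6.6.1 example, the result is 50 × 4 = 200 mg RP-3500 and 200 × 4 = 800 mg olaparib. The olaparib difference then vanishes and only the 1.6-fold RP-3500 difference remains. Column wording elsewhere in Table 13 is loose too: the olaparib cell for grade 4 neutropenia speaks of drug dosages.

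These points stand as limits on how often the cell matters. They do not make the row consistent. The schedule-first rule postpones the conflict until the dosage step, and individualization does not say which cell is correct. The general text does settle the order, but against the cell, which is the reason to correct it. The 1.6-fold RP-3500 difference holds under either comparator.

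**Conclusion.** The point holds: the grade 4 neutropenic fever row is wrong as written and should be corrected.

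At dose level 3 a literal reading gives 1.6 times the RP-3500 and two thirds of the olaparib per cycle that the protocol's own order gives. At dose levels -1, 1 and 2 it turns an available RP-3500 reduction into discontinuation. Both results assume that the dosage step has been reached, that the patient is still on the assigned Table 7 dose, and that the site follows the cell rather than the section 6.6.3 order.

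The number of patients affected cannot be estimated from the documents. Section 4.1 reports one grade 3 neutropenic fever outside the DLT window among the first five patients, on the earlier 3-days-per-week schedule, and no grade 4 case. No sample size, error rate or analysis changes; what is at stake is re-dosing after a serious toxicity.

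**What to change.** In the grade 4 neutropenic fever row of Table 13, RP-3500 column, replace olaparib dosages with RP-3500 dosages. Drug dosages would also do and would match the three other RP-3500 cells, but it leaves the order to the section 6.6.3 text, so naming RP-3500 is clearer. The olaparib cell can stay as it is, since its condition then refers to a reduction that the row actually orders.

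Optionally, add one sentence to section 6.6.1 saying that its examples, which lower both drugs at once, are permitted exceptions to the RP-3500-first order.

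The cost is one or two words in one table cell and, if wanted, one sentence. Design, sample size and analysis are unaffected.
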